3.16.2 Visit 2b

Once a subject is trained on the device, the subject will receive a single 40-minute therapy session with their Cala Trio. The subject will be asked to not stimulate at least 8 hours prior to this visit. The following assessments will be made prior to the therapy session and again immediately post the therapy session:

- Tremor assessments (while in the *off* state) including:
 - Modified MDS Unified Parkinson's Disease Rating Scale Part III (MDS-UPDRS) be rated by the PI
 - Bain & Findley Activities of Daily Living (ADL) upper limb subset score will be rated by the subject. The ADL assessment will be performed using the subject's own household props
- CGI-S, I/PGI-S, I
 - Clinical/Patient Global Impression of Severity (CGI-S/PGI-S): The investigator or designee (CGI) and Patient (PGI) will rate the overall tremor severity prior to stimulation
 - Clinical/Patient Global Impression of Improvement (CGI-I/PGI-I): The investigator or designee (CGI) and Patient (PGI) will rate the overall tremor improvement following stimulation

Additionally, the Cala Trio will direct the subject to perform the outstretched postural hold tremor tasks before and after the stimulation session to measure tremor power. Finally, subjects will input their Patient Session Impression of Improvement (PSI-I) rating on the device after the stimulation session

Visits 2a and 2b may be combined into a single Visit 2.

3.17 Home-Usage

A study of safety and efficacy of Transcutaneous Afferent Patterned Stimulation (TAPS) for reduction of action tremor in Parkinson's Disease (PD)	Protocol PD-02
	Rev A; 1-OCT-2020

The home use portion of the study will last 4 weeks. It will include:

- 2 stimulation sessions/day preferably at the same time every day-recommended as one in the morning and one in the evening.
- Motion Data on device before and after each stimulation session. Cala Trio will direct the subject to perform postural hold tremor tasks before and after the stimulation session to measure tremor power. Additionally, subjects will input their Patient Session Impression of Improvement (PSI-I) rating on the device after the stimulation session
- Weekly Bain & Findley Activities of Daily Living (ADL) upper limb subset score will be rated by the subject based on their recall of the previous week (no props will be used)
- Device factory reset of the Cala Trio will occur on Day 14 of treatment via a call with study staff

3.18 Visit 3/Study exit

Subjects will be reminded to be in the *off* state, i.e. to skip their last dose of PD medication, prior to their telemedicine Visit 3/Study exit. The subject will be asked to not stimulate at least 8 hours prior to this visit. The subject will receive a single 40-minute therapy session with their Cala Trio. The following assessments will be made prior to the therapy session and again immediately post the therapy session:

- Tremor assessments (while in the *off* state) including:
 - Modified MDS Unified Parkinson's Disease Rating Scale Part III (MDS-UPDRS) be rated by the PI
 - Bain & Findley Activities of Daily Living (ADL) upper limb subset score will be rated by the subject. The ADL assessment will be performed using the subject's own household props
- CGI-S, I/PGI-S, I
 - Clinical/Patient Global Impression of Severity (CGI-S/PGI-S): The investigator or designee (CGI) and Patient (PGI) will rate the overall tremor severity prior to stimulation
 - Clinical/Patient Global Impression of Improvement (CGI-I/PGI-I): The investigator or designee (CGI) and Patient (PGI) will rate the overall tremor improvement following stimulation
- Product/preference survey
- Subjects will return all study materials with provided shipping packages

A factory device reset and re-calibration may be required if the device does not prompt a tremor task measurement of postural hold prior to starting the stimulation session.

All subjects will be informed of their right to withdraw from the clinical study at any time without penalty or loss of benefits. The Investigator may prematurely discontinue any subject from the study if the Investigator feels that the subject can no longer fully comply with the requirements of the study or if any of the study procedures are deemed potentially harmful to the subject.

A study of safety and efficacy of Transcutaneous Afferent Patterned Stimulation (TAPS) for reduction of action tremor in Parkinson's Disease (PD)	Protocol PD-02
	Rev A; 1-OCT-2020

3.19 Subjects Compensation

In order to compensate subjects for their time and effort, they will be paid an amount as listed on the site-specific Informed Consent Form (ICF).

4.0 Schedule of Assessments

The following table outlines the schedule of assessment for subjects throughout the entire duration of the study.

Table 1. Schedule of Assessments

	Assessment	Visit 1 (screening/ enrollment)	Visit 2a/b (device calibration/ training)	Home Use	Visit 3 (Study Exit)	After device is returned to Cala
	Time	Day -7	Day -1/0 (+ 7 days)	Days 1-28	Day 28 (+ 7 days)	N/A
PI or designee	Informed Consent	X				
	Medical History & Demographics	X				
	Medication Review	X				
	UPDRS modified Part III	X				
	Confirmation of Subject Eligibility	X				

A study of safety and efficacy of Transcutaneous Afferent Patterned Stimulation (TAPS) for reduction of action tremor in Parkinson's Disease (PD)	Protocol PD-02
	Rev A; 1-OCT-2020

	UPDRS modified Part III (pre/post stim)		X		X	
	CGI-S/I		X		X	
Cala	Device Calibration & Training		X			
	Final device upload and device unassignment followed by factory reset			Factory reset on Day 14		X
Subject	Stimulation & PSI-I		X	2x per day	X	
	Kinematics		Pre/Post stim	Pre/Post stim	Pre/Post stim	
ALL	B&F ADLs (recall)	X		1x per week	X	
	B&F ADLs (pre/post stim)		X		X	
	PGI-S/I		X		X	
	Product Survey				X	
ALL	Adverse Events	X	X	X	X	

5.0 Risk and Benefit Assessment

5.1 Justification for the Study

While there are medications available to Parkinson's disease patients, they are not always effective in treating hand tremor. Another common treatment option is DBS, which, while effective, is highly invasive and risky. Therefore, effective alternative, non-pharmacologic treatment for Parkinson's disease may prove to be of value. The Cala Trio is a treatment alternative that is non-invasive, reversible, and potentially lower risk than currently available therapies.

5.2 Description and Analysis of All Potential Risks to Subjects

5.2.1 Risk Categories

Cala Health believes the investigational Cala Trio device and this study are *nonsignificant risk* as defined by the US IDE regulations (21 CFR 812).

5.2.2 Potential Risks and Protection against Risks

5.2.2.1 Potential Risks

The risks associated with the Cala Trio device are similar to those risks observed in the routine clinical use of commercially available transcutaneous electrical nerve stimulators (TENS devices) or cutaneous-placed electrodes. Cala Health's previous clinical study of a similar device showed a 2% chance of significant and persistent skin irritation (including redness, itchiness, and/or swelling), a 1% chance of stinging pain in the wrist, and a 1% chance of a feeling of weakness in the wrist. All incidences resolved without treatment or sequelae, and there were no serious adverse events.

Possible minor risks/adverse reactions that may occur with the use of the Cala Trio device and in this study are:

- Discomfort with stimulation (e.g. stinging, sensation of weakness, etc.)
- Allergic reaction to electrodes or other materials

A study of safety and efficacy of Transcutaneous Afferent Patterned Stimulation (TAPS) for reduction of action tremor in Parkinson's Disease (PD)	Protocol PD-02
	Rev A; 1-OCT-2020

- Skin irritation, including redness and/or itching

Possible adverse reactions that are more serious, but less likely to occur, with the use of the Cala Trio device and in this study are:

- Signs of significant skin irritation, sores, electrical burns or lesions at the site of stimulation
- Significant and persistent increase in muscle tightness or stiffness
- A feeling of chest pressure during stimulation
- Swelling of the arm, wrist, or hand

5.2.2.2 Protection against Risks:

The Cala Trio device will be used in the clinical study in accordance to the instructions for use provided with the investigational device. The instructions for use disclose the above risks and appropriate actions to take if these events should occur (e.g., stop using the device, notify the investigator, etc.).

Some subjects may find the tingling sensation from the stimulation to be unpleasant. To mitigate this risk, subjects will always have control over the stimulation level and may reduce or discontinue a stimulation level at any point in time.

To further minimize risk, subjects will be trained on device usage by a study staff member prior to using the device at-home and must demonstrate ability to successfully operate the device.

To mitigate the chance of adverse events occurring, all subjects participating in the study are evaluated and monitored during the study.

The relatively low current (≤ 8 mA) electrical stimulation administered in this study is applied to the wrist, away from vital organs such as the heart. Therefore, this study does not pose any electrical safety hazard to the subject.

5.2.3 Minimization of Risks

5.2.3.1 Design Considerations

Cala Health has designed the Cala Trio device to minimize the risk posed to study subjects. The stimulator pulses are safe, observe charge delivery thresholds and safeguards, and are within the range of those used clinically for TENS devices [24]. The Cala Trio device delivers lower levels of energy than many commercially available transcutaneous stimulation devices, so Cala Health expects fewer potential complications and risks for the Cala Trio device.

5.2.3.2 Stimulation- current unable to be delivered

If the Cala Trio device were to malfunction and electrical current could not be delivered, this would not present a potential for serious risk to the health, safety or welfare of the subject. The effect would be that the subject would not receive stimulation and would require returning the malfunctioning device to the study site.

A study of safety and efficacy of Transcutaneous Afferent Patterned Stimulation (TAPS) for reduction of action tremor in Parkinson's Disease (PD)	Protocol PD-02
	Rev A; 1-OCT-2020

5.3 Potential Benefits

The subject's hand tremor may improve while in this study; however, this will not be guaranteed or promised to a subject.

5.4 Alternatives for Participation

Subject participation in this study is voluntary. Should the subject elect not to participate, alternatives to participation include medications and/or surgical options.

6.0 Clinical Event Definitions and Reporting

6.1 Definitions

6.1.1 Adverse Event

An AE is any untoward medical occurrence, unintended disease or injury, or untoward clinical signs (including abnormal laboratory findings) in subjects, users or other persons, whether or not related to the investigational medical device.

6.1.2 Adverse Event Rate

The adverse event rate is defined as percentage of subjects who experienced an adverse event.

6.1.3 Serious Adverse Event

A SAE is an adverse event that either:

- Led to death
- Led to serious deterioration in the health of the subject, that either resulted in:
- A life-threatening illness or injury
- A permanent impairment of a body structure or a body function
- In-subject hospitalization or prolonged hospitalization
- Medical or surgical intervention to prevent life-threatening illness or injury or permanent impairment to a body structure or a body function
- Led to fetal distress, fetal death or a congenital abnormality of birth defect.

6.1.4 Unanticipated Serious Adverse Device Effect

An unanticipated serious adverse device effect (UADE) is a serious adverse effect, which by its nature, incidence, severity, or outcome has not been identified, in the current version of the risk analysis report.

An anticipated serious adverse device effect (ASADE) is an effect that by its nature, incidence, severity or outcome has been identified in the risk analysis report.

6.2 Adverse Event Reporting

AE information will be collected from subject enrollment through study exit. AEs that occur during this study should be treated by established standards of care that will protect the life and safety of the subject.

The Investigator will report any AEs to the Sponsor and will assess AEs for their relationship to the device and therapy, and whether or not the event meets the definition of

A study of safety and efficacy of Transcutaneous Afferent Patterned Stimulation (TAPS) for reduction of action tremor in Parkinson's Disease (PD)	Protocol PD-02
	Rev A; 1-OCT-2020

serious. Subsequent intervention required, resolution status and whether or not the AE resulted in the subject's discontinuation in the study will also be reported.

Any SAE or UADE must be reported to the Sponsor within 24 hours of knowledge of the event. The Investigator is responsible for notifying the Institutional Review Board (IRB), as required by the site-specific IRB requirements.

All AEs must be recorded, as applicable, on the case report forms provided.

6.3 Device Observations and Malfunctions

A device malfunction is defined as failure of an investigational medical device to perform in accordance with its intended purpose when used in accordance with the instructions for use.

All device malfunctions are required to be documented on a case report form, reported to the Sponsor and, if required, reported to the IRB within the required timeframe.

In the event of a suspected device malfunction or device observation, the device and accessories will be returned to the Sponsor for analysis. Instructions for returning the device will be provided by the Sponsor.

All device malfunctions will be evaluated by Cala Health staff. Serious injuries and/or deaths during the study will be evaluated to determine if the Cala Trio device might have malfunctioned or contributed to the event.

7.0 Data Quality Assurance

7.1 Data Collection and Storage

Data will be collected using case report forms (CRFs) designed specifically for this study. The data will be analyzed by Cala Health staff and reviewed by the investigators and a biostatistician, as needed. Investigators will be responsible for completion and timely submission of the forms to Cala Health for data processing.

Cala Health quality assurance procedures are designed to ensure that complete, accurate, and timely data are submitted, that protocol requirements are followed, and that complications and adverse device effects are reported. Incoming data are reviewed to identify inconsistent or missing data and adverse effects. Data problems will be addressed in calls to the investigational site and during site visits.

Collected data will be stored on paper documents or on a 21 CFR Part 11-compliant electronic data capture (EDC) system. All paper documents will be securely stored at the study sites. Each subject's data will be de-identified by assigning a unique identification number per subject. This identification number will be assigned by the researchers at the time of consent. The identification number will be securely stored at the study site, and only researchers involved in the study will have access to the information in the cabinet.

Investigators are to maintain all source documents as required by the protocol, including worksheets and Informed Consent forms. The source documents can be used by Cala Health staff (as needed) to verify information submitted on the CRFs.

A study of safety and efficacy of Transcutaneous Afferent Patterned Stimulation (TAPS) for reduction of action tremor in Parkinson's Disease (PD)	Protocol PD-02
	Rev A; 1-OCT-2020

8.0 Site Training

The Sponsor, or designee, is responsible for the training of clinical site personnel, including the Investigator, sub-investigator(s), research coordinator(s), and other participating site staff. The Sponsor will conduct initial training on Cala Trio use, data collection, proper reporting of AEs, compliance with the protocol, informed consent process and associated activities necessary to conduct this clinical study in accordance with the regulations and Good Clinical Practices.

8.1 Protocol Deviations

Any deviations from the study plan identified during monitoring visits or through other means will be documented on CRFs. These include, but are not limited to items such as the following:

- Failure to obtain written informed consent prior to conducting study related measurements
- Subject enrolled that does not meet inclusion/exclusion criteria
- Subject received stimulation using the wrong device (i.e. a right-handed device was used on the left wrist or a device of the wrong size was used)

If the study site demonstrates a pattern of consistent and frequent deviations, the Sponsor will undertake appropriate activities (e.g. re-training) to attempt to bring the site into compliance with the protocol. A pattern of repeated serious deviations from the protocol may result in site termination from the study.

9.0 Statistical Methods

9.1 General Principles

Standard summary statistics will be calculated for all study variables. For continuous variables, statistics will include means, standard deviations, medians and interquartile ranges. Categorical variables will be summarized in frequency distributions.

One-sided statistical tests will have p-values less than 0.025 deemed significant while two-sided tests will have p-values less than 0.05 deemed significant. Statistical analyses will be conducted in SAS version 9.3 or above (SAS Institute, Cary, N.C.), R version 3.2 or above (R Foundation for Statistical Computing, Vienna, Austria) or another validated statistical software package.

9.2 Safety Endpoint Analysis

The safety of the Cala Trio device will be evaluated by the incidence of device and therapy-related adverse events. Additionally, all adverse events documented during study conduct will be tabulated and reported.

9.3 Primary Effectiveness Endpoints Analyses

Primary endpoint for the study is defined as within subject comparison of tremor power before stimulation to after stimulation. Statistical testing of the primary endpoint will be

A study of safety and efficacy of Transcutaneous Afferent Patterned Stimulation (TAPS) for reduction of action tremor in Parkinson's Disease (PD)	Protocol PD-02
	Rev A; 1-OCT-2020

based on the cohort of all enrolled and treated subjects for whom outcome data are available.

The statistical objective related to the primary endpoint is to demonstrate that Parkinson's disease action hand tremor is reduced from pre-stimulation values at baseline to post-stimulation values at 4 weeks, under treatment with the Cala Trio device. Formally, the null and alternative hypotheses to be tested for each primary endpoint are as follows:

$$H_0: \mu_T \geq 0$$

$$H_A: \mu_T < 0$$

where μ_T is the change from pre-stimulation at baseline to post-stimulation at 4 weeks in the endpoint in question.

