Overview of Study Visits and Procedures	This study will include both subjects on levodopa and subjects taking other Parkinson's medications/unmedicated for Parkinson's. Subjects will be screened for eligibility and fitted with a Cala Trio device. Due to COVID-19 social distancing requirements, visits requiring physician or subject rated assessments will be conducted via telemedicine (i.e., video call). During Visit 1 (Day -7), enrollment will consist of subject eligibility/screening using clinician rated UPDRS assessments. During Visit 2a (Day -1), subjects will receive device training and calibration instructions. During Visit 2b (Day 0), UPDRS assessments and ability to conduct ADLs will be assessed pre and post stimulation session. Visits 2a and 2b may be combined into a single visit. Subjects will use Cala Trio at home for a period of 4 weeks (Day 1- Day 28). During Visit 3 (Day 28), the subjects will exit the study after a UPDRS and ADLs assessment pre and post stimulation session.
Efficacy Assessments	
 • Primary: Within subject comparison of tremor power before stimulation to after stimulation in dominant arm • Secondary: Within subject comparison of ADLs and UPDRS across Visits 1-3
Safety	The safety of the peripheral nerve stimulation will be characterized by the incidence of device and therapy-related adverse events
Number of Subjects	Up to 60 subjects
Number of Sites	1 site
Study Participation	The length of study participation is up to 6 weeks

Subject Population	
Inclusion Criteria	
Prospective subjects must meet all of the following criteria to be eligible for study participation:
 
 • Must be ≥ 22 years of age • Competent and willing to provide written, informed consent to participate in the study • Clinically significant postural tremor as defined by: 
 ◦ Dominant hand/arm exhibiting postural tremor ≥ 2 (while in the off state) as assessed by the MDS-UPDRS postural tremor score • Stable dose of Parkinson's disease medications, if applicable, for 30 days prior to study entry • Willing to comply with study protocol requirements including: 
 ◦ Having the ability to do telemedicine or video calls for study visits ◦ remaining on a stable dosage of Parkinson's medications, if applicable, during the duration of the study ◦ no significant caffeine consumption within 8 hours of study visits

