3.3 Primary Endpoint

The primary endpoint (definition below) of the study is a within-subject comparison of tremor power before stimulation to after stimulation, as captured by the Cala Trio device’s on-board accelerometer. Unless otherwise specified, “tremor frequency”, “tremor power” and “single-session kinematic response” are per-session metrics defined as follows:

- “Tremor frequency” is the frequency, in the 3 – 12 Hz range associated with Parkinson’s tremor, where the power spectral density (PSD) of a session’s pre-stimulation accelerometry data is largest.
- “Tremor power” is integral of the PSD of the tremor accelerometry data in the 3 Hz window centered on the session’s tremor frequency.

- “Single-session kinematic response” is defined as the pre-stimulation tremor power divided by the post-stimulation tremor power.

The primary endpoint, “kinematic response”, is defined as the per-patient median of single-session kinematic responses.

Patients will be included in the primary endpoint analysis only if they completed at least 10 therapeutic sessions that met the following data quality criteria:

- Session was started at least 2 hours after the completion of a previous session.
- Participant completed both pre- and post-stimulation motion recordings, that are each
 - sufficiently free of recording artifact, including accelerometer saturation
 - sufficiently free of motion artifact, as detected by excessive power outside the 3 – 12 Hz tremor range in the PSD.

Statistical testing of the primary endpoint will be based on the cohort of all enrolled subjects for whom outcome data are available. The statistical objective related to the primary endpoint is to demonstrate that action hand tremor severity in PD is reduced with the Cala Trio device. Formally, the null and alternative hypotheses to be tested for the primary endpoint is as follows:

$$H_0: M_T \geq 1$$

$$H_A: M_T < 1$$

where M_T is the median kinematic response captured over the 4-week study.

The primary endpoint is a continuous variable and will be summarized descriptively using log-transformed mean and standard deviation, median, and interquartile range (first and third quartiles). Hypothesis testing of the change score M_T will be performed using Wilcoxon’s signed-rank test.

The primary endpoint is met if the two-sided p-value is < 0.05 , such that the null hypothesis is rejected in favor of the alternative hypothesis. The study is successful if the primary endpoint is met.

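### The Protocol and SAP name different primary quantities for tremor power, SAP 3.3 prints its alternative hypothesis backwards, and the 90% power figure cannot be checked against the deciding test

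*Protocol*

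**What the plan says.** **Protocol.** The synopsis gives the primary efficacy assessment as "Within subject comparison of tremor power before stimulation to after stimulation in dominant arm", and the first sentence of 9.3 says much the same. The formal objective in 9.3 is narrower: to show that action hand tremor "is reduced from pre-stimulation values at baseline to post-stimulation values at 4 weeks, under treatment with the Cala Trio device". The parameter mu_T is that change, with H_0: mu_T >= 0 and H_A: mu_T < 0. Section 9.6 returns to improvement from before to after stimulation and names test levels of both 0.05 and 0.01.

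**SAP 3.3.** The single-session kinematic response "is defined as the pre-stimulation tremor power divided by the post-stimulation tremor power". The primary endpoint "is defined as the per-patient median of single-session kinematic responses". The hypotheses are H_0: M_T >= 1 and H_A: M_T < 1, where M_T "is the median kinematic response captured over the 4-week study". The test is Wilcoxon's signed-rank. The endpoint is met at two-sided p < 0.05, "such that the null hypothesis is rejected in favor of the alternative hypothesis". For description, the endpoint "will be summarized descriptively using log-transformed mean and standard deviation", together with median and quartiles. Patients enter the analysis "only if they completed at least 10 therapeutic sessions that met the following data quality criteria".

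**Power (Protocol 9.7, SAP 3.6).** Both rest on a paired difference test at alpha 0.01 against no change from baseline, 10% attrition and 34 to 50 subjects. The table gives N = 30 for four weeks. The SAP states 90% power and the Protocol at least 90%. SAP 3.6 says effect-size estimates follow, but the table holds only metric, p value and N.

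**The concern.** The Protocol's formal contrast combines the four-week shift in pre-stimulation tremor with the acute response at week 4. The SAP's ratio captures only the typical acute response within a session. A reader of Protocol 9.3 would expect a four-week test of tremor power. The SAP tests the corresponding contrast (Visit 2b pre-stimulation to Visit 3 post-stimulation) only for MDS-UPDRS and BF-ADL, as secondary endpoints 2a and 2b.

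The direction matters because the success rule refers to the alternative hypothesis by name, and SAP 3.4 allows secondary testing only if the primary endpoint is met. As printed, a real benefit lies inside the null hypothesis.

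The power statement matters because it is the only justification for the sample size, and its test and alpha are not those that decide the study.

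**Working it through.** **1. The two contrasts (assumed values).** Let a be post/pre within a session and s be week-4 pre-stimulation power divided by baseline pre-stimulation power. The Protocol contrast, as a fraction of baseline, is s × a at week 4. The SAP ratio is 1 / (typical a).

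| s | a at week 4 | typical a | Protocol: post at week 4 / baseline pre | SAP ratio |
|---|---|---|---|---|
| 0.80 | 0.80 | 0.80 | 0.80 × 0.80 = 0.64 | 1/0.80 = 1.25 |
| 1.00 | 0.80 | 0.80 | 1.00 × 0.80 = 0.80 | 1.25 |
| 1.25 | 0.80 | 0.80 | 1.25 × 0.80 = 1.00 | 1.25 |
| 1.00 | 0.90 | 0.80 | 1.00 × 0.90 = 0.90 | 1.25 |

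In the third row the Protocol contrast shows no change, while the SAP ratio shows a benefit.

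**2. Direction.** If tremor falls, post < pre, so pre/post > 1. The stated objective is reduction, which is M_T > 1. The printed H_A is M_T < 1. In simulation with log ratios normal at standardized mean d = 0.5 or 0.748 (true benefit), a one-sided test of the printed H_A at 0.025 rejected in 0 of 4,000 runs for each. The two-sided p-value does not depend on the printed inequality: at n = 30 and d = 0.748 in either direction it falls below 0.05 about 97% of the time. The printed direction therefore decides what a significant result means.

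**3. The plan's own figures.** Attrition reproduces: 30 / 0.9 = 33.3, rounded up to 34, and 50 × 0.9 = 45. The 90% does not reproduce, because no effect size or SD is printed. It can only be solved backwards. Suppose N = 30 means 90% power at 0.01, which the table does not say. Then the noncentral t equation P(T′ with 29 df and noncentrality d√30 > critical value) = 0.90 gives d = 0.748 (two-sided) or 0.692 (one-sided).

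**4. Power of the deciding test (illustrative).** Signed-rank at two-sided 0.05 on log ratios assumed normal, with d = mean / SD of the log ratio:

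| Assumed d | n = 30 | n = 45 |
|---|---|---|
| 0.5 | about 74% | about 89% |
| 0.69 | about 95% | about 99% |
| 0.75 | about 97% | about 99.8% |

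The last two rows reuse the plan's own 90% and are not independent evidence. The first row shows how far the answer moves with an effect the documents do not state.

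**5. Scale of the test.** The signed-rank test assumes symmetry about the null value, and a raw ratio is right-skewed when its log is symmetric. With normal log ratios and a true median ratio of 1, two-sided rejection at nominal 5% and n = 30 is:

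| Assumed SD of log ratio | Raw pre/post minus 1 | Log ratio |
|---|---|---|
| 0.1 | about 5% | about 5% |
| 0.3 | about 6% | about 5% |
| 0.6 | about 10% | about 5% |
| 1.0 | about 16% | about 5% |

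At SDs of 0.3 and above, the excess lies in the benefit direction (about 5%, 9% and 15%, against a nominal 2.5%). The raw result also depends on which way the ratio is written. At d = 0.69, SD 0.6 and n = 30, power is 98.6% for pre/post and 78.6% for post/pre, against 94.7% on logs either way. These are not size-adjusted; the apparent advantage of raw pre/post largely reflects its inflated size.

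**The case against.** **The intent is clear.** The objective sentence in SAP 3.3 says tremor is to be reduced, and the two-sided p-value ignores the inequality. Both points stand, so this is a wording correction. But the success rule invokes the alternative hypothesis, and as printed that alternative is worsening.

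**The Protocol already supports the SAP.** The synopsis, the opening of 9.3 and 9.6 do compare before with after stimulation. That narrows the conflict to the objective and mu_T in 9.3. None of these places gives a ratio, a median or a rule for combining sessions, so they do not amount to the SAP endpoint. SAP 3.9 lists average change in tremor power by week, but as an exploratory summary and not as the contrast in 9.3.

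**The power statement concerns the right endpoint.** SAP 3.6 says N is predicated on the primary endpoint, and the table row is kinematic measurements over four weeks. That is fair. The firm mismatches are the alpha and the named test. For the same effect, planning at 0.01 and testing at 0.05 is conservative. A reader might infer that the study is underpowered; the documents do not support that, because without an effect size the 90% cannot be refuted either.

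**The test scale is not stated.** SAP 3.3 mentions logs only for the descriptive summary. The literal reading is a test on the raw ratio, but a log-scale test is not excluded. A reader might infer that type I error is certainly inflated. That needs both the raw reading and enough skew; at a log-SD of 0.1 the problem has all but gone.

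**Conclusion.** Two contradictions are established from the text alone, without any assumption. The formal primary parameter in Protocol 9.3 is not the endpoint in SAP 3.3, and the SAP's alternative hypothesis points to worsening. How far the two contrasts would differ in this study is unknown; the figures above show only that they can differ.

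On power, the conclusion is limited. The 90% can be neither reproduced nor refuted, and the move from 0.01 to 0.05 is in the safe direction. The illustrative power, from about 74% to 97% at n = 30, rests on assumed values of d and on normal log ratios.

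On scale, the SAP should say what it tests. Null rejection on the raw ratio ranges from about 5% to about 16% at n = 30 for assumed log-SDs of 0.1 to 1.0.

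The SAP is dated February and March 2021, after the October 2020 Protocol, and the study is unblinded. A reader might infer that the endpoint was changed after data had been seen. The documents do not say so, but neither do they explain the change.

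**What to change.** 1. Correct SAP 3.3 to H_0: M_T <= 1 and H_A: M_T > 1. Define success as two-sided p < 0.05 with the effect in the benefit direction.
2. Reconcile Protocol 9.3 and SAP 3.3 on one primary quantity. If the SAP endpoint is kept, amend the objective and mu_T in 9.3 to match it, and declare the change with its date, its reason and whether outcome data had been seen.
3. State that the signed-rank test is run on the log of each patient's median ratio against 0. Rewriting the ratio as post/pre without taking logs is not an equivalent repair.
4. Say which of 0.05 and 0.01 in Protocol 9.6 decides. Restate Protocol 9.7 and SAP 3.6 for the deciding test and alpha, with the assumed effect, its SD and the expected loss to the 10-session rule, which the 10% attrition is not said to cover.

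**Cost:** a protocol amendment, SAP wording, a declared test scale and a rewritten power paragraph. No new visits or measurements. Nominal power on logs will look lower than on the raw pre/post ratio, but mostly because the raw test rejects too often under the null.
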